Cover Page	1
Official Study Title:	2
Effect of Low-Dose Caffeine on Performance in Elite Sitting Volleyball Players	3
NCT Number:	4
NCT number pending	5
Date of Document:	6
June 28, 2025	7
	8
	9
	10
	11
	12
	13
	14
	15
	16
	17
	18
	19
	20
	21
	22
	23
	24
	25
	26
	27
	28
	29
	30
	31
	32
	33
	34
	35
	36

Materials and Methods

37

Participants

38

Thirteen elite male sitting volleyball players (29.84 ± 11.50 years) from the 2024 Paravolley European Champion Turkish Sitting Volleyball Men's National Team participated in this study. as the inclusion criteria were: (1) having a minimum level of disability according to the World ParaVolley classification, (2) not having any neuromuscular or musculoskeletal disorders that would prevent participation in the measurements, (3) not smoking or consuming alcohol, and (4) not using any ergogenic support to increase performance in the last 3 months. Exclusion criteria were: (1) failure to complete all test sessions, (2) occurrence of injury or illness during the study period that could affect performance and (3) changes in habitual caffeine consumption during the study.

45

All athletes were given detailed information about the study, their voluntary participation was ensured, and an informed consent form was obtained before any measurement. The study was approved by the Sinop University Human Research Ethics Committee (approval no: 2025/91) and was conducted in accordance with the ethical standards of the Declaration of Helsinki [19]. This study adheres to the Consolidated Standards of Reporting Trials (CONSORT) guidelines to ensure transparency and comprehensive reporting of the randomized controlled trial design and methodology (Figure 1).

50

[figure not shown]

Figure 1. CONSORT flowchart of the study

51

[figure not shown]
Study Design

52

[figure not shown]
This study had a randomized, double-blind, counterbalanced, and cross-over design. Athletes participated in a total of three sessions (one familiarization session and two test sessions) (Figure 2). Participants were randomly divided into two groups ($n=7$ and $n=6$) using a computer-based random number generator (simple randomization, 1:1 ratio), one group receiving low-dose caffeine (L-CAF) and the other group receiving placebo (PLA) As required by the design, each participant received both supplements, but the order of supplementation was randomized. A 48-hour washout period was given between each test sessions. All measurements were performed at the same time interval (e.g., 09:00 - 10:00) to minimize the possible effects of circadian rhythm differences. Participants were asked not to change their eating habits, to avoid intense exercise, and to consume alcohol during the study. They were also advised to maintain their individual daily caffeine consumption habits. Moreover it taken all participants daily caffeine consumption survey before sessions.

53

54

**Figure 2.** Test Protocol

In each test session, participants consumed a randomly assigned supplement containing caffeine (LCAF) or placebo (PLA) with 250 ml of water 45 minutes before the tests. All participants completed a standard warm-up protocol which consisted of a 5-minute low-intensity general warm-up, followed by 10 minutes of dynamic stretching and technical work, 15 minutes before the test. After the warm-up period, athletes performed the serve speed, spike speed, and speed-endurance performance tests, respectively. In the serve and spike speed tests, each athlete performed three trials, and the highest value was recorded. Participants were given a 30-second rest period between trials and a 2-minute rest period between tests (Figure 3.). Rating of Perceived Exertion (RPE) during the speed-endurance course were recorded using the Borg 6-20 scale immediately at the end of the test. Caffeine and placebo doses were prepared using an analytical laboratory balance (Shimadzu, Tokyo, Japan) capable of measuring to within precision of 1 mg, and Oxford brand pure caffeine powder (ISO 14001; The Oxford Vitality Health Company Ltd; London, UK) and polydextrose was used throughout the study.

**Figure 3.** Timeline of Daily Experimental Procedures**Data Collection Tools***Serve Speed*

The serve speed of sitting volleyball players was evaluated with a standardized measurement protocol within the framework of World ParaVolley game rules and court dimensions. Participants positioned themselves on the service line with their hips touching the court surface and used a serve. During the test, participants were instructed to hit the ball within the target area at the highest possible speed appropriate to their individual techniques. Each participant was given three attempts, and the best score was recorded. Serve speed measurements were performed with a high-precision handheld radar (Bushnell Velocity Speed Gun, USA). 83
84
85
86
87

Spike Speed

The spike performance was performed by positioning the participants in front of the net in accordance with the real conditions in the game. The participants were instructed to hit the ball at the highest speed possible into the 3×3 m target area. The spike speed measurements were performed with a high-precision handheld radar (Bushnell Velocity Speed Gun, USA). The data were recorded in miles. 88
89
90
91
92

Speed-Endurance Performance

The speed and endurance test developed by Marszalek et al. (Figure 4) was applied with a single-trial protocol to evaluate the anaerobic endurance capacity of the athletes [7]. The test begins with athletes in a seated position behind the starting point at cone A. The participants completed the specified route by moving back and forth between cones A, B, C, D, E and G respectively in the shortest time possible in accordance with the requirements of the test. All athletes were required to maintain physical contact with the base of each cone throughout the test. The results were measured precisely by the Optojump photocell system (Microgate, Bolzano, Italy) mounted on a tripod. 93
94
95
96
97
98
99

[figure not shown]

Figure 4. Speed-Endurance Test Parkour

102

Data Analysis

103

All data are reported as mean \pm standard deviation (Mean \pm SD). Normality of distribution of data was assessed by Shapiro-Wilk normality test. Paired t-test was applied to examine the differences between LCAF and PLA conditions in serve speed, spike speed and speed-endurance performance. Power analysis was conducted using G*Power for a paired-samples t-test (two-tailed, $\alpha = 0.05$, $n = 13$, power = 0.80). Cohen's d coefficient was calculated for effect sizes and interpreted according to the following classification: insignificant (<0.2), small (0.2-0.5), medium (0.5-0.8) and large (>0.8) [20]. Statistical significance was accepted as $p < 0.05$. All analyses were performed using IBM SPSS Statistics 25.0 (IBM Corp., Armonk, NY, USA) software.

104

105

106

107

108

109

110

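### Do exclusions for illness or changed caffeine intake, decided after randomisation, put the paired comparison at risk?

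*Combined protocol and SAP*

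**What the plan says.** The Participants section gives three exclusion criteria. The first is "failure to complete all test sessions"; the other two are "2) occurrence of injury or illness during the study period that could affect performance and (3) changes in habitual caffeine consumption during the study". Because non-completion has its own criterion, the second and third can also apply to an athlete who finished both test sessions.

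The same section reports "Thirteen elite male sitting volleyball players", states adherence to CONSORT and refers to a flowchart (Figure 1), which is not reproduced in the text available.

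Study Design says "This study had a randomized, double-blind, counterbalanced, and cross-over design". It reports groups of 7 and 6 and adds that "each participant received both supplements, but the order of supplementation was randomized". On caffeine intake it says "They were also advised to maintain their individual daily caffeine consumption habits" and "Moreover it taken all participants daily caffeine consumption survey before sessions".

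Data Analysis specifies a paired t-test for serve speed, spike speed and speed-endurance. Its power statement is two-tailed, with alpha 0.05, n = 13 and power 0.80, and gives no effect size. It does not define an analysis population.

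**The concern.** Exclusions that operate after randomisation deserve scrutiny, above all when they rest on judgement. Whether an illness could have affected performance is a matter of opinion, and no amount defines a change in caffeine habit. The survey before the second test session comes after the first supplement, so criterion 3 may draw on information gathered once treatment has begun. The trial is called double-blind, but the blinded roles are not named, and masking of treatment order would not hide the performance results.

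Two things could go wrong. If the supplement caused the event, removal would be related to the athlete's own caffeine-placebo difference and the mean difference would be biased, in either direction. If someone decided after seeing the results, the freedom to keep or drop an athlete would raise the type I error even where the illness had nothing to do with treatment. With 13 athletes, one removal is 1/13 = 7.7% of the sample.

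**Working it through.** **Counts.** Participants: 13 took part. Study Design: 7 + 6 = 13 allocated, each receiving both supplements. Data Analysis: n = 13 for power. The figures agree and leave no room for a visible removal.

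**The plan's own power figure.** With no effect size stated, 0.80 can only be matched by solving for the standardised paired difference dz. For a two-sided paired t-test with 12 degrees of freedom and non-centrality dz × √13, power 0.80 requires dz = 0.847. At that dz and n = 12, power is 0.761. Result-independent loss of one athlete therefore costs about 0.04 in power and causes no bias.

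**Removal related to the difference.** Let SD_d be the standard deviation of the caffeine-placebo differences, and let ρ be the correlation between an athlete's difference and his propensity to be removed. The documents give no value for ρ, so a range is assumed. Removing the lowest of 13 on that propensity shifts the mean of the other 12 by ρ × 1.668/12 = 0.139ρ SD_d, where 1.668 is the expected extreme of 13 standard normal values. Simulation under no effect (400,000 replicates) gives:

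| ρ | Shift in mean (SD_d) | Type I error |
|---|---|---|
| 0 | 0 | 0.050 |
| 0.3 | 0.04 | 0.053 |
| 0.5 | 0.07 | 0.060 |
| 1.0 | 0.14 | 0.097 |

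Negative ρ mirrors these values. The last row is the bound for one removal and one endpoint.

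**Unrelated illness: fixed rule against free choice.** Take one athlete whose illness is unrelated to treatment and falls at random on either session (null simulation, 1,000,000 replicates):

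| Shift in his difference | Always kept | Always dropped | Whichever gives p < 0.05 |
|---|---|---|---|
| none | 0.050 | 0.050 | 0.063 |
| 2 SD_d | 0.048 | 0.050 | 0.070 |

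Either fixed rule holds the nominal level. Only choosing between them after seeing the results inflates it.

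**Power of the two fixed rules at dz = 0.847.**

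| Shift in his difference | Power, kept | Power, dropped |
|---|---|---|
| 0 | 0.80 | 0.76 |
| 1 SD_d | 0.77 | 0.76 |
| 2 SD_d | 0.69 | 0.76 |
| 3 SD_d | 0.57 | 0.76 |

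An athlete 2 SD_d off moves the mean by 2/13 = 0.15 SD_d if kept. Up to a shift of about 1 SD_d, keeping him is no worse than dropping him; beyond that, dropping him has more power.

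**Timing of criterion 3.** The only stated source is a survey taken before sessions, so the last one precedes the last test. A change found then is known before that athlete's caffeine-placebo difference exists. If acted on at once, he would lack a second session and fall under criterion 1. A results-aware removal needs a delayed decision, which the text does not rule out but nowhere suggests.

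**The case for a change.** The best case for a change is that it is cheap and principled. The main test would include every randomised athlete with both sessions. Those meeting criterion 2 or 3 would be dropped only in a sensitivity analysis, and the numbers excluded would be stated. This needs no new measurements, only some wording and a repeat of three t-tests. It would remove discretion in a sample where one athlete matters, and it fits the stated adherence to CONSORT. Calling the trial double-blind does not fully answer the point, because it does not say who was blinded and cannot mask performance results.

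Part of this stands. The criteria have no threshold, can reach completers, and carry no statement on masking to results. A sentence giving the number excluded under each criterion, or saying that none was, would be good reporting.

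The case for a different main analysis does not stand. Leaving out athletes who were ill or whose caffeine intake changed is a reasonable choice in a physiological cross-over, and as a fixed rule it is valid. Reversing it gives up power when the illness effect is large. The document describes a study that appears complete, so redefining the analysed set and setting a caffeine threshold now would themselves be choices made after the fact.

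**Conclusion.** No change to the plan is needed. The criteria are loosely worded, but every visible count is 13, and with no removal the effect on the result is exactly zero. The error rates of 0.063 to 0.097 require something the documents do not show: an athlete removed because the supplement affected him, or a decision taken with the results in hand. Replacing the stated exclusions with an all-completers main analysis is a trade-off rather than a correction, since both fixed rules control the type I error and dropping has the higher power once the illness effect exceeds about 1 SD_d.

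What remains is reporting detail that Figure 1 may already supply. Had a completer been removed, an analyst would ordinarily say so and show the tests with and without him, leaving the stated main analysis as it is.

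These conclusions rest on normally distributed differences, one endpoint at a time, at most one athlete affected, an assumed range for the correlation, and the visible counts being those analysed. If a completer was in fact removed with knowledge of the results, the point would have to be reopened.

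### The crossover is called counterbalanced but orders were assigned by simple randomisation, and the planned paired t-test ignores the two order groups; at the reported 7/6 split the cost is power, not bias.

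*Combined protocol and SAP*

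**What the plan says.** Study Design opens with "This study had a randomized, double-blind, counterbalanced, and cross-over design". The same paragraph reports "Participants were randomly divided into two groups ($n=7$ and $n=6$) using a computer-based random number generator", followed by the description "simple randomization, 1:1 ratio". It adds that "each participant received both supplements, but the order of supplementation was randomized". No block, permuted list or fixed order total is described.

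There are two test sessions after one familiarisation session, and on spacing the plan says "A 48-hour washout period was given between each test sessions".

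Data Analysis states: "Paired t-test was applied to examine the differences between LCAF and PLA conditions", for serve speed, spike speed and speed-endurance alike. It names no session, order or carryover term. The power statement gives a two-tailed alpha of 0.05, n = 13 and power 0.80, without an effect size.

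**The concern.** Two things do not fit.

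**Wording.** Counterbalancing means that the two orders are equalised by design. Simple randomisation assigns each athlete independently and equalises nothing except in expectation. The two terms cannot both describe how the 7/6 split was reached, and a reader cannot tell which one does.

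**Analysis.** In a two-session crossover, anything that shifts performance between sessions (learning, residual fatigue, conditions on the day) pushes the caffeine-placebo difference one way in athletes who had caffeine first and the other way in those who had it second. A plain paired t-test pools the 13 differences as if they shared one mean. The part of the shift that does not cancel becomes bias, and the part that does cancel in the mean still inflates the standard deviation. With 13 athletes there is little power to spare.

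**Working it through.** **Inputs from the documents.** 13 athletes (Participants); order groups of 7 and 6, two test sessions, simple randomisation (Study Design); paired t-test, two-tailed alpha 0.05, n = 13, power 0.80 (Data Analysis).

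**Input not in the documents.** The session effect. I write it as a shift of ±π in the caffeine-placebo difference, in units of the within-order SD of those differences, and use 0, 0.25, 0.5 and 1.

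**1. The plan's power figure.** It cannot be reproduced, because no effect size is given. Solving the noncentral t for 80% power at n = 13 (12 df) gives an implied standardised difference dz = 0.847, which is used below.

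**2. Chance of 7/6 under simple randomisation.** 2 × C(13,7) / 2^13 = 2 × 1716 / 8192 = 0.419. A split of 8/5 or worse has probability 1 − 0.419 = 0.581.

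**3. Bias at 7/6.** The mean of the 13 differences carries π × (7 − 6)/13 = π/13, or 7.7% of the session effect. For π = 0.5 that is about 0.04 SD. A forced 7/6 list would leave the same 7.7%.

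**4. Inflation of the error variance at 7/6.** The between-order sum of squares adds 4 × 7 × 6 / 13 × π² = 12.92π². Divided by 12 df, the expected variance of the differences becomes 1 + 1.077π²:
- π = 0.25: 1.067
- π = 0.5: 1.269
- π = 1: 2.077

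**5. Session-adjusted estimate.** Average the two order-group means of the differences. The shifts +π and −π cancel exactly. Its standard error is s × ½√(1/7 + 1/6) = 0.2782s, against s/√13 = 0.2774s for the plain mean, with s pooled within order on 7 + 6 − 2 = 11 df.

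**6. Simulation at 7/6** (normal differences, at least 100,000 replicates per setting). A range shows the two possible directions of the session effect.

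| Session effect (SD) | Type I error, plain | Power at 0.847, plain | Type I error, adjusted | Power at 0.847, adjusted |
|---|---|---|---|---|
| 0 | 5.0% | 0.80 | about 5% | 0.79 |
| 0.25 | 4.4% | 0.76-0.80 | about 5% | 0.79 |
| 0.5 | 3.1% | 0.68-0.76 | about 5% | 0.79 |
| 1 | 0.8% | 0.39-0.58 | about 5% | 0.79 |

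The plain test does better in the direction in which the 1/13 leak adds to the caffeine effect, and worse in the other.

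**The case against.** A reader might infer that simple randomisation left this trial with unbalanced orders and a raised false-positive rate. Under more lopsided draws the plain test does go wrong: at 10/3, for example, 54% of a session effect leaks into the estimate, and at an assumed 0.5 SD type I error is 11%. The documents do not support that reading here. The sentence that names simple randomisation also reports 7 and 6, the best balance possible with 13. At that split the test is conservative. Averaged over all the splits that simple randomisation can produce, its type I error stays between 4.98% and 5.11% for session effects of 0.25 to 1 SD.

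It can also be said that the power loss comes from leaving out a session term, not from the allocation method, and would arise under a blocked list too. That is correct. It means that changing the allocation would repair nothing at 7/6, and that the analysis is what needs changing.

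Finally, the session effect is an assumption, and the plan takes steps to limit it: a familiarisation session, a fixed time of day and avoidance of intense exercise. If it is zero, the plain test is better by about one point of power. This stands, and is why the point is about precision and reporting. It does not remove it: the documents give no grounds for taking the effect as zero, and the insurance is cheap.

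**Conclusion.** The point holds as a contradiction in reporting and a weakness in the analysis, not as a serious bias. The terms counterbalanced and simple randomisation cannot both be true of the allocation. At 7/6 the bias is 1/13 of any session effect. The paired t-test loses little power at 0.25 SD (0.76-0.80 against 0.79 adjusted), 3 to 11 points at 0.5 SD (0.68-0.76), and 21 to 40 points at 1 SD (0.39-0.58).

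This rests on four assumptions:
- The groups of 7 and 6 are the two order groups as analysed, with no athlete dropped after allocation. The text supports this but does not spell out the sequences, and the flow and protocol figures were not available.
- The session effect lies between 0 and 1 SD of the paired differences.
- The differences are normal with equal variance in both orders.
- There is no unequal carryover between orders, which the session term would not remove.

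**What to change.** **Data Analysis.** For all three outcomes, replace the plain paired t-test with the session-adjusted crossover analysis: the average of the two order-group means of the caffeine-placebo differences, with pooled within-order variance on 11 df. The same result is the intercept from regressing the difference on order coded −1/+1, which SPSS can fit. If results have already been seen, report the plain test alongside and label the change as such.

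**Study Design.** State how the 7/6 split arose. Delete the word simple if the split was forced, or counterbalanced if it came about by chance. A restricted list of exactly 7 and 6 is relevant only if allocation is still open; writing it in after a simple allocation would misreport what was done.

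**Cost.** One sentence in each section and one degree of freedom (12 to 11). If there is no session effect, power falls from 0.80 to 0.79. No extra athletes or procedures are needed.

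### Does the Study Design sentence on eating, exercise and alcohol contradict the inclusion criteria in a way that matters?

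*Combined protocol and SAP*

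**What the plan says.** Two places in the combined protocol and SAP mention alcohol.

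- **Participants** (Materials and Methods) lists it as an inclusion criterion: "3) not smoking or consuming alcohol". No time window is attached. The next criterion in the same list does have one: "4) not using any ergogenic support to increase performance in the last 3 months".
- **Study Design** describes how athletes were asked to behave: "Participants were asked not to change their eating habits, to avoid intense exercise, and to consume alcohol during the study".

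The sentence after that deals only with caffeine: "They were also advised to maintain their individual daily caffeine consumption habits". Among the exclusion criteria, the only one about consumption also concerns caffeine: "3) changes in habitual caffeine consumption during the study". Participants further reports that "All athletes were given detailed information about the study" and that consent was obtained before any measurement.

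**The concern.** As punctuated, the word *not* in the Study Design sentence applies only to eating habits. The other two items are then positive requests, and the last one asks athletes to drink. Athletes admitted as non-drinkers could not comply and still match the description under which they were enrolled.

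Letting *not* run through the whole list does not repair the sentence. The alcohol item then agrees with the criterion, but athletes would be asked not to avoid intense exercise.

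The criterion cannot simply stand in for the missing rule, because it governs entry and says nothing explicit about the test period. If athletes really had been asked to drink around the sessions, the serve-speed, spike-speed and speed-endurance results could have been disturbed, and a reader repeating the study would copy a wrong instruction. If the same wording had been used in the information for athletes, the error would have reached them.

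**Working it through.** No figure in the plan depends on this sentence, so the check is textual.

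**Where the terms occur.** In the readable text, alcohol is mentioned twice: once in inclusion criterion (3) and once in the Study Design sentence. Exercise is mentioned once, in that same sentence. Data Collection Tools and Data Analysis mention neither. Figures 2 and 3 (the test protocol and the daily timeline) and the consent pages are not available in this copy, so these counts describe the visible text only.

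**Possible readings of the sentence.**

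| Reading | Eating habits | Intense exercise | Alcohol | Against criterion (3) |
|---|---|---|---|---|
| *not* applies to the first item only | unchanged | avoid | consume | conflicts |
| *not* applies to all three items | unchanged | do not avoid | do not consume | agrees |
| *avoid* carries over from exercise to alcohol | unchanged | avoid | avoid | agrees |

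The first reading is the strict grammatical one, and it is the only one that conflicts with another statement in the document. The second agrees on alcohol. Its exercise item is implausible, but no other text contradicts it. The third is unidiomatic, because the comma and the repeated *to* work against it. It is also the only reading that is both sensible in all three items and consistent with the criterion.

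**Is a slip plausible?** Yes. Other sentences have similar faults: the lead-in to the inclusion criteria begins in mid-clause with a lower-case letter, and the sentence on the daily caffeine survey in Study Design lacks a workable verb. A misplaced verb in a list fits that pattern better than a deliberate request that non-drinkers should drink.

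**What kind of text is it?** Study Design is written in the past tense and reports what athletes were asked. It is not the wording handed to them, which belongs to the participant information that Participants says was given before measurement.

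**Does anything in the analysis depend on it?** Data Analysis compares caffeine with placebo by a paired t-test on n = 13, two-tailed, α = 0.05, power 0.80. For athlete *i* the quantity tested is dᵢ = (caffeine result)ᵢ − (placebo result)ᵢ. The instruction, whatever it was, is stated once for the whole study and does not differ by condition. It enters neither the formula nor the power statement, and rewording it leaves n, α, the stated power and the test as they are.

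**The case for a change.** The best case for acting runs as follows. The sentence is complete and current, with no gap or redaction to excuse it. Reaching a sensible meaning requires mentally altering the words. In the visible text it is the sole account of the in-study request on both alcohol and exercise. The document says it follows CONSORT for the sake of transparent reporting, yet a reader cannot take the conduct rules from it as printed. The remedy would be one sentence and one check against what athletes were told.

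Most of this stands. The wording is wrong, the conflict with the criterion is real on a literal reading, and the correction would be cheap.

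Two parts do not carry the weight placed on them. Calling the sentence an operative instruction goes further than the text allows, since it narrates the methods and there is no sign that athletes acted on it. Calling it the sole statement holds only for what can be read here, because either missing figure or the participant information may state the rule clearly. The possibility that the same error reached athletes cannot be excluded from these documents, but nothing in them suggests that it did.

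**Conclusion.** The concern is right about the wording and does not call for a change to the plan. It is a clerical slip in one 20-word sentence. The Study Design sentence and inclusion criterion (3) should be reconciled as ordinary copy-editing, with the sponsor and the investigator confirming what the 13 athletes were told. This review does not say what that instruction should be.

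The effect on design, sample size, analysis and inference is nil as far as the documents show. No alcohol intake is reported, no difference between the caffeine and placebo conditions is implied, and no number in the plan moves.

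The conclusion rests on two assumptions: that the information actually given to athletes did not repeat the literal wording, and that the unseen figures and consent pages do not contradict the criterion. If athletes had in fact been asked to drink, the matter would be one of study conduct and would need a fresh look. Nothing in the readable text points that way.

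### The only treatment test in this 7/6 two-session crossover is a paired t-test with no period term, which loses power if the shift between sessions is moderate or large.

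*Combined protocol and SAP*

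**What the plan says.** Study Design describes the trial as follows: "This study had a randomized, double-blind, counterbalanced, and cross-over design". There are two test periods: "Athletes participated in a total of three sessions (one familiarization session and two test sessions". On order, it states that "each participant received both supplements, but the order of supplementation was randomized". Allocation was done "using a computer-based random number generator (simple randomization, 1:1 ratio" and produced groups of 7 and 6.

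Data Analysis then names a single treatment comparison: "Paired t-test was applied to examine the differences between LCAF and PLA conditions in serve speed, spike speed and speed-endurance performance". Its power statement is for the same paired test (two-tailed, alpha 0.05, n = 13, power 0.80) and gives no effect size. Nowhere do the documents mention a period, session or sequence term, a check for order effects, or a mixed model. Cohen's d is to be reported and labelled in bands, with large meaning above 0.8, but the SD that standardises it is not stated.

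**The concern.** The design varies the order of the supplements on purpose, and the analysis then ignores that order. Suppose performance changes between session 1 and session 2 whatever the supplement, through learning, fatigue or differing conditions. Athletes who took placebo first have the change added to their caffeine-minus-placebo difference; athletes who took caffeine first have it subtracted. Counterbalancing nearly cancels it in the mean. It remains in the SD of the differences, which is the error term of the paired test.

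What is at stake is a missed effect and a wider interval, not a false positive. With 13 athletes and 80% power only for a large effect, there is little power to spare. If Cohen's d uses the SD of the differences, a shift also tends to shrink it and can change its label.

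**Working it through.** **Inputs from the documents.** n = 13; sequence groups of 7 and 6; two-sided alpha 0.05; power 0.80; paired t-test.

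**Assumed inputs.** The effect size and the session shift are not given. The effect is back-solved from the power statement. The shift π (session 2 minus session 1) is shown as a range, in units of SD_d, the SD of the within-athlete differences net of period.

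**Step 1: the plan's power figure.** With 12 df and noncentrality dz√13, 80.0% power requires dz = 0.847 (0.847 × √13 = 3.05). The stated 80% cannot be checked independently, because no effect size accompanies it.

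**Step 2: model.** With SD_d = 1, the caffeine-minus-placebo difference has mean τ − π when caffeine came first and τ + π when placebo came first.

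- Bias of the overall mean: (7 − 6)π/13 = π/13 in absolute value. This is 0.019, 0.038 and 0.077 SD_d at π = 0.25, 0.5 and 1.0.
- The residual sum of squares is noncentral chi-square with 12 df and λ = 4 × 7 × 6 × π²/13 = 12.92π².
- The expected variance of the differences is therefore 1 + 12.92π²/12. This is 1.27 at π = 0.5 and 2.08 at π = 1.0.

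**Step 3: paired test given 7/6.** Numerical integration against t(0.975, 12), at τ = 0.847. *Worse* means the imbalance pulls the mean towards zero; *better* means it pushes it away.

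| Shift π (SD_d) | Type I error | Paired power, worse to better | Adjusted power | Gain from adjusting (points) |
|---|---|---|---|---|
| 0 | 5.0% | 80.0% | 79.1% | −0.9 |
| 0.1 | 4.9% | 79.0-80.4% | 79.1% | +0.1 to −1.3 |
| 0.25 | 4.4% | 76.1-79.8% | 79.1% | +3.0 to −0.7 |
| 0.5 | 3.1% | 67.7-76.0% | 79.1% | +11.4 to +3.1 |
| 1.0 | 0.8% | 39.1-58.3% | 79.1% | +40.0 to +20.8 |

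**Step 4: period-adjusted test.** The estimate is the average of the two sequence means. Its standard error is ½ × s_p × √(1/7 + 1/6) = 0.278 s_p, on 11 df, where s_p is the pooled within-sequence SD. Power is 79.1% and type I error 5.0% at any shift, because the shift cancels from the estimate and is absent from s_p.

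**Step 5: break-even.** The adjusted test has more power above a shift of 0.09 in the worse direction, 0.32 in the better direction, and about 0.17 on average. In the better direction the paired test keeps at least 80.0% power up to a shift of about 0.23.

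**Step 6: interval width.** The expected 95% CI half-width is 0.599 SD_d for the adjusted analysis. For the paired analysis it is 0.592 at shift 0, 0.612 at 0.25, 0.667 at 0.5 and 0.858 at 1.0. At 0.5 the paired interval is about 11% wider (0.667/0.599 = 1.11); at 1.0 it is 43% wider.

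**Step 7: Cohen's d, if it uses the SD of the differences.** At a true dz of 0.847 the chance of the label 'large' is 58% with no shift, 52-57% at 0.25, 41-50% at 0.5 and 14-27% at 1.0. At 0.5 'large' is still the most likely label.

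**Step 8: other true effects, shift 0.5.** At dz = 0.5, paired power is 25.3-33.9% against 37.5% adjusted. At dz = 1.0 it is 83.0-88.5% against 90.4%.

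**The case against.** **The paired test is not wrong.** With no shift it is valid, and with a shift it is conservative given 7/6. This is a choice between two valid tests, and neither wins everywhere. That stands, and it limits the point to efficiency.

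**The shift is unknown and may be small.** The trial has a familiarisation session, a fixed time of day and a standard warm-up. On conduct it says: "Participants were asked not to change their eating habits, to avoid intense exercise". On measurement: "In the serve and spike speed tests, each athlete performed three trials, and the highest value was recorded". The athletes are an elite national squad, and injury, illness or changed caffeine habits during the study lead to exclusion. A shift of 1.0 SD_d would exceed the assumed caffeine effect itself. All of this makes a large shift less likely, and the 1.0 row should be read as an extreme. It does not show that the shift is negligible. The speed-endurance test, which "was applied with a single-trial protocol to evaluate the anaerobic endurance capacity of the athletes", lacks the best-of-three safeguard. None of these controls takes a remaining shift out of the error term, and the plan does not estimate it.

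**The 0.847 may be on another scale.** The dz in a paired power calculation could refer to differences that already include the shift. If so, paired power is 79.0-85.4% at a shift of 0.5 and 81.7-91.8% at 1.0, so it stays near or above the stated 80%. This is fair: the fall below 80% depends on the scale chosen. The case for adjusting does not, because the adjusted test then reaches 87.7% and 97.8%, gains of 2.3-8.7 and 6.0-16.1 points.

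**A post hoc change adds flexibility.** The document is in the past tense, so the results may already be known. That is a reason to disclose the change and show both analyses.

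**Conclusion.** The concern holds. The plan's only treatment comparison leaves any session shift in its error term, although the trial randomised order and could remove it.

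The harm is lost power and wider intervals. False positives are not inflated, so a significant paired result is not undermined, and the bias from 7/6 is small. On the net-of-period scale, the paired test trails the adjusted one by 3.1-11.4 points at a shift of 0.5 SD_d. At 0.25 the comparison runs from 3.0 points in favour of adjusting to 0.7 against; below about 0.17 adjusting gains nothing on average.

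The conclusion rests on the assumed range of shifts, on dz = 0.847, and on normal differences with equal variance in both sequences. The absence of a period term is certain; the size of any loss in this trial is not. It should be fixed because the remedy is cheap and the possible loss is much larger than the cost.

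**What to change.** For serve speed, spike speed and speed-endurance, make the period-adjusted crossover analysis the main one. Compare session-1-minus-session-2 differences between the two sequences with a two-sample t-test and halve the contrast (11 df). Equivalently, fit a mixed model with fixed treatment, period and sequence and a random athlete effect.

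- Report the treatment difference with its 95% CI, and the period estimate.
- State which SD standardises Cohen's d.
- Keep the paired t-test as a sensitivity analysis.
- If the data have already been analysed, describe the adjusted analysis as post hoc and show both results.

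The cost is one degree of freedom and about 0.9 points of power if there is no shift (80.0% to 79.1%). Each athlete's allocated order is needed; the randomisation must have produced it, and I assume it is in or can be linked to the dataset, which the documents do not say. The change may mean a disclosed reanalysis and not only new wording. It does not address carryover.
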